#### 3.2 Secondary Objectives

2. To evaluate changes in signs and symptoms of opioid withdrawal, opioid craving, level of awareness (activation/sedation) after administration of 32 mg BUP SL, and other medication effects during the index ED visit using validated subjective and objective instruments and physiologic measures.
3. To evaluate the safety of rapid induction via adverse events checklist prior to conclusion of the ED index visit.
4. To assess the duration of effect of BUP 32mg SL on treating opioid withdrawal and craving (days 1-3).
5. To assess patient experience domains related to treatment satisfaction and acceptability using self-reported measures and collecting data on reasons for non-participation in study amongst potentially eligible patients (at each assessment, Days 0-3 and 30).
6. To collect preliminary data and explore the treatment effect on linkage to treatment, quality of life and additional patient-level outcomes (drug use, overdose events, healthcare use) at 30 days.

#### Exploratory Analyses:

To evaluate participants’ pre-study opioid use characteristics (opioid type [fentanyl or not], averaged daily quantity, route of administration) and other patient-level characteristics to explore their potential effect outcomes.

## 4 Study Design and Endpoints

### 4.1 Description of Study Design

This is an open-label, single arm, single site feasibility and acceptability study in which 35 ED patient-participants who have untreated moderate to severe OUD and are experiencing opioid withdrawal (COWS score  $\geq 8$ ). will receive treatment in the ED with a loading dose of BUP 32mg SL (administered in divided doses) at their index visit. We will assess the feasibility, acceptability, safety, and utility of this intervention and provide preliminary data on the effect on opioid withdrawal, craving, and sedation as well as additional patient-level outcomes (engagement in treatment, drug use, quality of life, healthcare utilization).

The first assessment will occur in-person in the ED at the index visit (day 0), and 4 additional appointments will be scheduled: 3 research visits and one follow-up care appointment with an OUD provider. Research assessments will be conducted in-person at clinical research space on Bellevue/NYULH campus on days 1-3, and by phone on day 30. Patients will be provided with appointment reminder cards with the time and location of their next appointment, and the contact information for the research study team. At the conclusion of their day 3 visit, participants will be given a prescription for BUP SL 16mg per day with a quantity sufficient to last until their scheduled clinical follow up appointment for ongoing treatment. The prescription will be provided earlier, at the day 1 or day 2 research visit, if the participant reports opioid withdrawal and/or craving and has objective signs of withdrawal at that time.

### 4.2 Data Collection and Study Measures:

Procedures for data collection, data management, monitoring of data quality and data analysis have been developed and refined in our previous studies. These procedures include utilization of a computerized data base system (REDCap) to monitor clinical and research activities, including enrollment, adherence to treatment interventions, and completion of scheduled assessments.

The study team will assess a range of pretreatment participant characteristics, process measures, and outcome using validated, reliable instruments that are widely-used, primarily derived from previous and ongoing studies. We will collect data and reason for non-inclusion for participants who are approached but not enrolled. The research team will obtain data by participant self-report, EHR abstraction, and contact with treatment providers. Multiple secondary endpoints using a wide-range of subjective and objective measures will be collected in-person at the index visit (day 0) and visits on days 1-3, and by phone at day 30. Details on each study visit are described in Section 7.4 (Study Schedule).

#### 4.2.1 Study Measures

Study Measures will be selected from the Study Measures List (attached).

## 5 Study Endpoints

### 5.1.1 Primary Study Endpoints

#### 1. To estimate the proportion having “*successful rapid induction*”

*Successful Rapid Induction*, the primary study endpoint, is defined as completing rapid induction with a loading dose of BUP SL 32mg without experiencing a clinically significant serious and/or severe adverse event (AE) related to the intervention – specifically, the receipt of a dose of BUP SL greater than 8mg during the Index ED visit. We will determine the proportion of participants who have successful rapid induction during the ED index visit amongst all study participants.

- *Clinically significant adverse events* (AEs) include the following: over-sedation (defined as requiring invasive or non-invasive ventilator support, having a Richmond Agitation-Sedation Scale (RASS) of  $\leq -3$ , and/or clinician determination), hemodynamic instability (e.g., persistent hypotension not attributed to other causes), development of severe precipitated withdrawal

Study Number: s19-01700

Version: 7.0

Version Date: 08/01/2022

(clinician determination), or experiencing other unexpected, SAEs, related to receipt of the second dose of BUP SL (for a total of BUP SL 32mg) as defined in *Section 8.1*. This measure will be assessed at the end of the ED index visit.

- Precipitated withdrawal: Clinicians will assess whether an event is considered precipitated withdrawal. This clinical determination will be based on the severity of the withdrawal signs and symptoms, the rapidity of the onset of withdrawal symptoms, and clinical factors (e.g. timing since last use of an opioid agonist(s), type(s) of opioid agonist, duration of action of opioid agonist(s) used, and route of administration). Scores will be based on objective components, eliminating nausea which can be a side effect of BUP administration. Patients who experience precipitated withdrawal will be treated with ancillary medications.

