#### 3.1 Primary Objective

1. To estimate the proportion and confidence intervals of participants who have “*successful rapid induction*” (as further defined below) amongst enrolled participants who receive a loading dose of BUP SL 32mg during the ED index visit. Successful rapid induction is defined only be the outcome of the participant’s visit, and not by any following research visits.

Hypothesis: All participants who receive a loading dose of BUP SL 32mg will have successful rapid induction. Successful rapid induction is defined as receiving a total of 32 mg of buprenorphine SL at the index research visit without experiencing a clinically significant serious and/or severe adverse event related to the intervention. Loss to follow up in subsequent research visits will not impact this outcome measure.

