#### **6.9.1 Formulation, Appearance, Packaging, and Labeling**

All BUP ordered as part of clinical care in the EMR and supplied through the Bellevue Hospital Clinical Pharmacy and NYULH Clinical Pharmacy. Currently on Bellevue Hospital formulary is the generic buprenorphine/naloxone (8mg/2mg) tablet and Subutex brand BUP monoproduct (the latter would be for use in patients/participants with a naloxone allergy only). The manufacturer will depend on what is currently on the hospital formulary and may change. Should this occur, participants will receive the equivalent medication dose. For example, if the formulary changes from BUP-NX (8mg/2mg) tablet to buprenorphine/naloxone (8mg/2mg) film, the participant will receive buprenorphine/naloxone (8mg/2mg) film sublingually (same bioavailability/dose).

Participants will also receive a prescription for BUP to pick up at their preferred outpatient pharmacy either after the third research visit, or when they demonstrate objective signs of withdrawal.

There will be no storage or administration of medication by the research pharmacy.

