### **6.9.4 Dosing and Administration**

All participants will receive a total dose of BUP 32mg sublingually in divided doses during the index ED visit. After the participant has received a total of 8mg (as a single dose or in divided doses), BUP SL 24mg will be administered (i.e., 8mg + 24mg, or 4mg + 4mg +24mg). A dose of up to BUP 8mg SL may be administered by the clinical provider prior to enrollment of the patient-participant (i.e., given clinically, not as a research procedure).

After pre-medication assessments are complete and the participant is confirmed to have a COWS of  $\geq 8$ , the participant will be given BUP SL to reach a dose of 8mg. Starting 30 minutes after BUP administration, the participant will be reassessed for withdrawal severity and any adverse events. As long as there are no unexpected significant adverse events, an additional BUP 24mg SL will be administered. Then, participants will be monitored and reassessed every 30 minutes for a period of at least 90 minutes after receiving the last dose of BUP.

Participants will return on days 1, 2, and 3 for research visits. At those visits, participants will be assessed for opioid withdrawal using the COWS scale. On the first day that the participant has objective signs of opioid withdrawal (via COWS), the [name], who is a licensed physician with an X-waiver for BUP prescription, or another study clinician (with the appropriate license and X-waiver) will electronically send a prescription the participant's preferred outpatient pharmacy for a daily dose of BUP 16mg (BUP or BUP/NX 8/2mg: two SL) to start immediately. Participants will be prescribed a quantity sufficient to ensure medication coverage until the date of their appointment for ongoing treatment with a (non-study) OUD treatment provider. Participants who do not exhibit opioid withdrawal at any of the visits on days 1-3, will be given a prescription upon completion of the day 3 visit with instructions to self-administer upon emergence of symptoms of opioid withdrawal or craving.

All participants will receive a referral to be seen by a provider experienced in treating OUD. Thereafter, continued treatment and specific daily dosage of BUP-NX will be a joint decision between the study participant and the healthcare provider.

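### The primary endpoint sentence carries two dose figures (32 mg and more than 8 mg), and Sections 3.1 and 5.1.1 use different denominators, so the scoring of a partly dosed participant is not settled

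*Combined protocol and SAP*

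**What the plan says.** Section 5.1.1 says that the primary endpoint "is defined as completing rapid induction with a loading dose of BUP SL 32mg", without a clinically significant serious or severe adverse event "related to the intervention – specifically, the receipt of a dose of BUP SL greater than 8mg" during the index ED visit. The closing clause in full is "the receipt of a dose of BUP SL greater than 8mg during the Index ED visit". The section takes the proportion over everyone in the study.

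Section 3.1 defines the same endpoint as "receiving a total of 32 mg of buprenorphine SL at the index research visit" without such an event. It takes the proportion "amongst enrolled participants who receive a loading dose of BUP SL 32mg during the ED index visit", and it hypothesises that every such participant will succeed.

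Three other places bear on the reading:

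- The adverse-event bullet in Section 5.1.1 ties the qualifying events to the second dose. Section 6.7.1 treats the first 8 mg as standard care and only the following 24 mg as the thing under evaluation.
- Section 6.9.4 describes a 32 mg total over the index ED visit. It lets a clinician give up to 8 mg "prior to enrollment of the patient-participant (i.e., given clinically, not as a research procedure"), with the study topping up to 8 mg and then giving 24 mg.
- Section 10.1 names the primary outcome only as the proportion successfully induced by the loading dose. It gives no rule for totals between 8 and 32 mg.

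**The concern.** The trial has one primary endpoint, and the sentence that defines it contains two dose figures. If the closing clause is coded as the completion rule, someone who took 16 or 24 mg in total is a success in Section 5.1.1 and is not one in Section 3.1. If the clause only explains which adverse events count, both sections require 32 mg and there is no conflict over dose.

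The denominators conflict on either reading. Under Section 3.1 the participant must have received 32 mg to be counted at all, so the dose part of the definition is met by construction and the proportion reflects only adverse events. Under Section 5.1.1 a participant who did not complete the load stays in the denominator.

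The study asks whether the full load can be delivered in the ED, and its hypothesis is that all recipients succeed. One participant whose category depends on the reading is therefore enough to change the headline result. The study is open label, so leaving the choice until the data have been seen would allow the more favourable reading to be picked.

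**Working it through.** There is no power or effect-size figure to reproduce: Section 10.1 bases the sample size of 35 on feasibility. The check has two steps.

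**Step 1. Score dose histories under each reading** (assuming no qualifying adverse event).

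| Dose history (mg) | ED visit total | 5.1.1, clause = completion rule | 5.1.1, clause = event attribution | 3.1 |
|---|---|---|---|---|
| 8 + 24, all after enrolment | 32 | success | success | success |
| 8 clinical, then 24 | 32 | success | success | success if counted over the ED visit, as in 6.9.4 (24 after enrolment) |
| 4 clinical, then 4 + 24 | 32 | success | success | as above (28 after enrolment) |
| 8 + 16 of the 24 | 24 | success | not a success | not a success; outside the denominator |
| 8 + 8 of the 24 | 16 | success | not a success | not a success; outside the denominator |
| 8 only | 8 | not a success | not a success | not a success; outside the denominator |

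The dose rules part only for totals above 8 mg and below 32 mg. Such totals can arise only if the 24 mg step is started and not finished. Section 6.9.1 lists a "generic buprenorphine/naloxone (8mg/2mg) tablet" on the current formulary, so 24 mg would be 24/8 = 3 units and partial intake is possible. The documents give no frequency for it.

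**Step 2. Size.** Section 3.1 asks for confidence intervals but names neither method nor level. I assume exact (Clopper-Pearson) 95% limits. For x successes in n, the lower limit is the 0.025 quantile of Beta(x, n − x + 1); when x = n this is 0.025^(1/n).

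Take n = 35 with no qualifying event, and let k participants have totals above 8 mg but below 32 mg. The value of k is an assumption. For k = 2:

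- Clause as completion rule, all participants: 35/35 = 100%; lower limit 0.025^(1/35) = 90.0%.
- 32 mg rule, all participants: 33/35 = 94.3%; lower limit from Beta(33, 3) = 80.8%.
- 32 mg rule, Section 3.1's denominator: 35 − 2 = 33, so 33/33 = 100%; lower limit 0.025^(1/33) = 89.4%.

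Over a range of k (lower limits in brackets):

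| k | Clause as completion rule | 32 mg rule, all 35 | 32 mg rule, 3.1 denominator |
|---|---|---|---|
| 0 | 100% (90.0) | 100% (90.0) | 100% (90.0) |
| 1 | 100% (90.0) | 97.1% (85.1) | 100% (89.7) |
| 2 | 100% (90.0) | 94.3% (80.8) | 100% (89.4) |
| 3 | 100% (90.0) | 91.4% (76.9) | 100% (89.1) |
| 5 | 100% (90.0) | 85.7% (69.7) | 100% (88.4) |

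With all 35 in the denominator, each participant who changes category moves the estimate by 1/35 = 2.9 points.

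**The case against.** The strongest reply is that the clause was never a completion rule. It directly follows the reference to the intervention and reads naturally as explaining it: dosing beyond the standard 8 mg. The sentence has already stated its dose criterion of 32 mg, and the adverse-event bullet and Section 6.7.1 both treat the second dose as what is being tested. This stands as a reading at least as good as the other. A reader might infer that Section 5.1.1 definitely scores 16 or 24 mg as a completed load; the documents do not support that. The reply does not remove the problem, because the clause sits inside the definition of success and states receipt of a dose within a visit, and no other text says which meaning governs.

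A reader might also infer that participants given 8 mg clinically before enrolment must fail Section 3.1, since they receive only 24 mg afterwards. Section 5.1.2 does describe the index visit as running from enrolment, but it does so to set the window for repeated secondary assessments. Section 6.9.4 builds the clinical dose into the 32 mg, and Section 3.1 itself also speaks of the ED index visit. Failing these participants would be a strained literal reading, and the documents do not say how many would be pre-dosed. What stands is a loose term, *index research visit*, that should be tidied.

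It is also fair that the disputed group may be empty. The 24 mg is planned as one step, and anyone who stops before it fails under every rule. The study is a descriptive pilot with no numerical success threshold.

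**Conclusion.** The point holds as an unresolved ambiguity in the primary endpoint together with a plain conflict of denominators. It is not a demonstration that the two sections score participants oppositely. On one tenable reading of Section 5.1.1, a total above 8 mg but below 32 mg is a success; under Section 3.1 it is not, and by that section's own denominator such a participant is left out altogether.

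A reader might take 33/35 to be the result under Section 3.1. It is not: that figure combines the 32 mg rule with Section 5.1.1's denominator, whereas Section 3.1 as written gives 33/33. The sizes rest on assumed counts of partly dosed participants, no qualifying adverse events, 35 participants in all, and exact 95% limits. If nobody is partly dosed, the dose readings agree; the denominators still differ for anyone who stops at 8 mg or less.

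**What to change.** Reconcile Sections 3.1, 5.1.1, 6.7.1 and 6.9.4 before analysis:

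1. State one dose-completion criterion for scoring the endpoint, in the same words in Sections 3.1 and 5.1.1.
2. If the more-than-8 mg clause is meant for attributing adverse events, move it to the adverse-event bullet and say so there.
3. In Section 3.1, replace *index research visit* with *index ED visit*, and state that buprenorphine given clinically before enrolment counts towards the total, as Section 6.9.4 already implies.
4. Use one denominator, all study participants as in Section 5.1.1. Participants who do not meet the stated criterion are then scored as not completed and listed with the total received and the reason.

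The cost is endpoint wording only. The reported proportion may come out slightly less favourable. No dose or clinical rule changes.

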### 5.1.2 Secondary Study Endpoints

#### 1. To evaluate opioid withdrawal, opioid craving, sedation during of index ED visit:

We will estimate the change in signs and symptoms of opioid withdrawal, opioid craving, level of awareness (activation/sedation) and other medication effects at repeated points of assessment during the index ED visit (spanning from enrollment in the study to a minimum of 90 minutes after the second dosage of BUP) using validated subjective and objective instruments and physiologic measures. For each domain (withdrawal, craving, sedation), we will determine the proportion of participants who experience changes in the specified measures and assess the magnitude of change and the time to change comparing repeated measures assessed during the index visit before treatment, after the first dose of BUP, and after the second dose of BUP.

The primary measures for opioid withdrawal and craving will be the Clinical Opiate Withdrawal Scale (COWS) and Opiate Craving Scale (OCS), respectively. Complete or near complete relief of withdrawal and craving will be assessed primarily by the point at which patient reports this endpoint ("Tell me when your withdrawal/craving has gone away completely"); we will secondarily note when patient has COWS score, Likert, or VAS score indicating absence of withdrawal or craving. Near complete relief will be assessed secondarily as "gone away almost completely" and using a COWS score of <3. Oversedation will be defined clinically as the need for non-invasive or invasive ventilation to maintain adequate oxygenation and ventilation; the Richmond Agitation Sedation Scale (RASS) will be used secondarily to assess level of awareness (the spectrum of sedation to agitation). Relief of (or recovery from) sedation is when invasive or non-invasive ventilator support is no longer required, with a RASS > -2, and when patient is alert enough for discharge as determined by the treating clinician. Specific measures and times of assessment are further described in and Section 4.2.1 (Study Measures) and Section 7 (Study Procedures).

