This study offers patients FDA-approved BUP SL treatment for opioid dependence. As such, the potential risks of study participation are chiefly consistent with the usual care and use of these medications in everyday care practice – with the aforementioned small potential increased risks of over-sedation and precipitated withdrawal and those of data collection (time and effort, confidentiality). As described above, BUP exhibits a known ceiling effect on respiratory depression, which makes it remarkably safe compared to other opioids, even at high doses. The pharmacologic properties of BUP, the demonstration of safety of the higher initial dose strategy in a case series of 94 ED patients and in other clinical trials (as described in Sections 2.1.1-2.1.3 our plan to administer BUP in divided doses (as opposed to a single large dose) and the extended duration of clinical monitoring in a clinical setting fully equipped to address all potential adverse events, as well as the rigorous participant selection criteria are protective factors. More specifically, in order to minimize physical risks, patients who consent to participation and receive 32mg will be monitored closely every 30 minutes for at least 90 minutes (instead of 30-60 minutes as per clinical practice for ED-initiated BUP) using objective and subjective assessments by trained personnel. Naloxone (opioid reversal agent) will be available if patients begin to exhibit any signs or symptoms of respiratory depression or over-sedation. Patients will be screened prior to enrollment for history of adverse/allergic reactions to buprenorphine or any other opioids. They will be excluded from participation if they have history of adverse reaction. If patients begin to experience any signs or symptoms of allergic reaction, the appropriate medications and equipment will be available. Patients will be discharged with close follow-up and assessment (as part of the study), which will minimize any physical risks of BUP treatment.

To minimize any discomfort associated with reporting on sensitive behaviors, participants will be informed that they may refuse to answer questions that they are not comfortable answering. Questions related to eligibility determination and monitoring of safety and treatment response are not optional. If individuals

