#### **7.7 Rescue Medications, Treatments, and Procedures**

The ED setting and clinical staff are well-equipped to manage all potential adverse events associated with the study. Patients/Participants may receive treatment for other medical conditions and/or ancillary treatment for symptoms of opioid withdrawal (e.g., nausea, muscle aches) or sedation as clinically indicated in accordance with standard clinical practices. All medications, treatments, and procedures will be delivered as part of the clinical care of the ED visit.

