## **8.2 Classification of an Adverse Event**

### **8.2.1 Severity of Event**

AEs are graded according to the following scale:

**Mild:** An experience that is transient, and requires no special treatment or intervention. The experience does not generally interfere with usual daily activities. This includes transient laboratory test alterations.

**Moderate:** An experience that is alleviated with simple therapeutic treatments. The experience impacts usual daily activities. Includes laboratory test alterations indicating injury, but without long-term risk.

**Severe:** An experience that requires therapeutic intervention and/or interrupts usual daily activities. If hospitalization (or prolongation of hospitalization) is required for treatment it becomes an SAE.

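### The secondary over-sedation definition counts only need for ventilation and so leaves out naloxone-reversed events; the primary leaves them to clinician judgment without criteria, and the two definitions disagree

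*Combined protocol and SAP*

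**What the plan says.** Over-sedation is defined twice, in different terms.

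- **Secondary endpoint (section 5.1.2, item 1).** "Oversedation will be defined clinically as the need for non-invasive or invasive ventilation to maintain adequate oxygenation and ventilation". The RASS "will be used secondarily to assess level of awareness (the spectrum of sedation to agitation"), with no cut-off for over-sedation, and the definition has no clinician route. Recovery is also tied to ventilation: "Relief of (or recovery from) sedation is when invasive or non-invasive ventilator support is no longer required", together with a RASS above -2 and fitness for discharge in the clinician's view.
- **Primary endpoint (section 5.1.1).** Over-sedation is one of the clinically significant adverse events that defeat successful rapid induction: "over-sedation (defined as requiring invasive or non-invasive ventilator support, having a Richmond Agitation-Sedation Scale (RASS) of" -3 or lower, "and/or clinician determination), hemodynamic instability" and so on. Clinician determination is thus a third route to over-sedation.

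Naloxone appears in the risk-protection text of section 2.1.6: "Naloxone (opioid reversal agent) will be available if patients begin to exhibit any signs or symptoms of respiratory depression or over-sedation". The rescue section (7.7) does not name it, but allows treatment of withdrawal symptoms "or sedation as clinically indicated in accordance with standard clinical practices". Neither over-sedation definition, the recovery definition nor the rescue section says how naloxone use is to be counted.

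**The concern.** Section 2.1.4 names over-sedation as one of two known risks of buprenorphine and says the higher dosing may increase it. It is therefore the safety outcome on which this study of a 32 mg loading dose most needs a reliable count.

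Reversal with naloxone can become available earlier in the course of an event than the need for ventilation. If it works, ventilation may never be needed. A binary label that depends on ventilation then records no over-sedation in a participant who was treated for it. The primary endpoint can record the event, but whether it does depends on an unguided judgment in an open-label, single-arm study (section 10.2.1).

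The hypothesis in section 3.1 is that every participant who receives 32 mg will have a successful induction, so the classification of a single event decides whether the data agree with it. The results are also meant to inform clinical protocols and larger trials, so an undercount would carry forward.

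**Working it through.** The plan gives no figure to reproduce. Section 10.1 describes a purely descriptive analysis, with the sample size based on feasibility. The check has two parts.

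**1. Score test cases under each definition.**

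Case A: a participant receives 8 mg and then 24 mg, is given naloxone for over-sedation, has no recorded RASS of -3 or lower, and is never ventilated. Case B: a participant has a recorded RASS of -3, with no ventilation and no naloxone.

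| Route | Case A | Case B |
|---|---|---|
| 5.1.2 item 1: need for ventilation | Not met | Not met |
| **Secondary result** | **Not over-sedated** | **Not over-sedated** |
| 5.1.1: ventilator support | Not met | Not met |
| 5.1.1: RASS -3 or lower | Not met | Met |
| 5.1.1: clinician determination | Open, no criteria | Not needed |
| **Primary result** | **Either** | **Over-sedated** |

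Case A shows the naloxone gap. Case B shows that the two definitions disagree even without naloxone.

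Case A could also reach the primary endpoint through adverse-event grading, because success requires no related serious and/or severe event. Section 8.2.1 defines Severe as "An experience that requires therapeutic intervention and/or interrupts usual daily activities", which would fit. The Moderate grade in the same section, for events relieved by simple treatment, would fit as well. The medical-judgment criterion for a serious event in section 8.1.2 is a further possible route. Each of these is again a judgment.

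By contrast, section 5.1.1 lists factors to guide clinician determination of precipitated withdrawal (severity, speed of onset, timing and type of opioid). It gives none for over-sedation.

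Scheduled assessments are every 30 minutes (sections 2.1.6 and 6.9.4), so sedation treated between two of them may leave no low RASS score.

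**2. Illustrate the size.**

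Inputs: n = 35 (section 6.4). The number of naloxone-reversed events is assumed, since the documents give no rate. Intervals are exact Clopper-Pearson, two-sided 95%. For x events in n, the lower limit is the 0.025 quantile of Beta(x, n - x + 1) and the upper limit is the 0.975 quantile of Beta(x + 1, n - x).

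- One event is 1/35 = 2.9 percentage points.
- Success 35/35: lower limit 0.025^(1/35) = 0.900, giving 90.0 to 100%.
- Success 34/35 = 97.1%: 85.1 to 99.9%.
- Success 33/35 = 94.3%: 80.8 to 99.3%.
- Over-sedation 0/35: upper limit 1 - 0.025^(1/35) = 0.100, giving 0 to 10.0%.
- Over-sedation 1/35 = 2.9%: 0.07 to 14.9%.
- Over-sedation 2/35 = 5.7%: 0.7 to 19.2%.

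The chance of at least one such event among 35 is 1 - (1 - p)^35. For assumed true rates p of 1%, 2%, 5% and 10% it is 29.7%, 50.7%, 83.4% and 97.5%.

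**The case against.** The strongest reply is that the event is unlikely to disappear.

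- A clinician who gives naloxone for over-sedation has in effect judged over-sedation to be present, so the clinician route in section 5.1.1 fits the case closely.
- The severe and serious adverse-event criteria offer further routes to a primary failure.
- Section 5.1.2, item 1, also analyses sedation as a domain, with changes in the measures and time to change. Item 2 adds repeated vital signs, level of awareness and an adverse-event checklist. Section 8.3 requires all adverse events to be documented, and section 10.1 has them tabulated and described.
- Section 2.1.6 says only that naloxone will be available; it sets no rule for giving it.
- The one ED series described (Safety text in section 2.1.3), a chart review of 94 patients given 24 to 32 mg, reports no clinically significant sedation.

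Most of this stands, and it limits the point. A reader might infer that the study cannot detect a naloxone-reversed event, or that the primary endpoint rests on ventilation and RASS alone. The documents support neither: the clinician route is there, and safety reporting can capture the event. A reader might also infer that naloxone would routinely be given before either threshold is reached. The text supports only that it could be.

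Two things are not answered. The binary over-sedation label in section 5.1.2 has no route for the event. In section 5.1.1 the outcome depends on a judgment without stated criteria, and the adverse-event grades do not settle it, because Moderate and Severe are both open.

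**Conclusion.** The point holds in limited form. Applied as written, the secondary definition scores a participant who is reversed with naloxone and never needs ventilation as not over-sedated. The primary definition can count that participant but does not say when it should. The two definitions also differ on RASS and on clinician determination. This is an endpoint-classification problem in a dose-relevant safety outcome; it does not show that the event would go unrecorded.

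The size is conditional. The intervals assume 35 analysed participants, an event after the full 32 mg, no other failures and, for the primary endpoint, that no judgment-based route would otherwise have counted the event. With one event the lower limit for success falls from 90.0% to 85.1%. The analysis is descriptive with no decision threshold, so the effect is on what is reported and carried into later planning, not on a test result.

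**What to change.** Use one over-sedation definition in sections 5.1.1 and 5.1.2, item 1: ventilator support, RASS of -3 or lower, clinician determination, or receipt of naloxone for respiratory depression or over-sedation. Record the indication when naloxone is given, so that the last route can be applied. Tabulate naloxone use, and flag RASS and vital signs recorded after it so that they are not read as untreated values.

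This changes event counting only. It says nothing about when naloxone should be given.

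The cost is small: a shared definition in two sections and one table. Section 7.5 already calls for concomitant prescription medications to be recorded in REDCap. The downside is a possibly slightly lower success proportion.
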